Development of a weight maintenance intervention for bariatric surgery patients

Title: Development of a weight maintenance intervention for bariatric surgery patients

Principal Investigator: [name]

Co-Investigators: [name]; [name]; [name]; [name], PhD

Purpose. Bariatric surgery is the most effective treatment for patients with severe obesity, defined as class II obesity (body mass index [BMI] 35-39.9 kg/m²) with an obesity-related comorbidity or class III (BMI \geq 40 kg/m²) obesity. When compared to non-surgical treatment options, bariatric surgery results in greater weight loss, comorbidity remission, and quality of life improvement, and is associated with an extended lifespan. Many patients regain weight following bariatric surgery, which is associated with recurrence of obesity-related comorbidities such as diabetes. A major factor in undesirable weight regain is suboptimal patient adherence to post-operative dietary and physical activity recommendations. To improve patient adherence to recommended lifestyle behaviors, effective behavioral interventions are needed.

In this pre-post, within-subject pilot study, we will enroll Veterans one year following bariatric surgery and deliver an abbreviated behavioral weight loss maintenance intervention for 16 weeks. Specific aims are:

Aim 1: Refine telephone intervention scripts to address dietary, mobility, and behavioral issues specific to bariatric surgery patients.

Aim 2: Evaluate feasibility of conducting a multi-site trial, as indicated by recruitment and outcome assessment rates.

Aim 3: Evaluate intervention acceptability, as indicated by intervention adherence rates, pre-post changes in weight and process measures, and feedback from post-intervention qualitative interviews.

The VA performs ~450 bariatric operations per year across 17-21 sites. In a recent State-of-the-Art Conference on weight management co-led by Health Services Research and Development (HSR&D) and by our operations partner, the National Center for Health Promotion and Disease Prevention (NCP), the bariatric surgery committee strongly agreed that future priorities for VA include increasing the number of sites that offer bariatric surgery and identifying strategies to help veterans maintain weight loss resulting from surgery. Our intervention, if effective, can help increase VHA's return on investment as the bariatric surgery volume increases over the next decade.

Background and Significance. Our conceptual model (Table 1) specifies cognitive and behavioral factors involved in initiation and maintenance of health behaviors. This model was used to design the weight loss initiation and maintenance interventions of the two-phase MAINTAIN trial, which involved a weight loss initiation program followed by randomization to maintenance intervention or usual care among patients losing at least 4 kg in the initiation phase. In modifying the intervention for bariatric surgery patients, there will be a health behavior initiation phase to ensure that patients initiate the recommended health behaviors (e.g., increased protein intake, elimination of high-calorie beverages, monitoring of caloric intake). Following initiation of these health behaviors, the interventionist will teach patients skills to maintain those new habits, thereby reducing weight regain.

Table 1: Initiation and Maintenance Constructs

Initiation	Maintenance
Self-regulatory focus: approach a more favorable health state	Self-regulatory focus: avoid reverting to a less favorable health state
Favorable expectations about future outcomes of the behavior change	Satisfaction with outcomes of the behavior change
Action self-efficacy	Maintenance and recovery self-efficacy
Goal setting/action planning	Maintenance and relapse prevention planning
Monitoring by interventionist and self	Self-monitoring
Social support derived from social network, interventionist, and other participants	Social support derived primarily from social network

Design. This pilot study will be a within-person, pre-post design involving a 16-week intervention delivered starting one year after surgery (Figure 2). Patient outcomes will be assessed at baseline and 16 weeks. Participants will continue usual follow-up care with their primary care physician.

Figure 2: Study flow

We will recruit patients from four VA sites that perform bariatric surgery (Table 2).

Table 2: Bariatric Surgery Sites Agreeing to Participate in Pilot Intervention Study

VA Hospital	VISN	2015 Bariatric Surgery Volume	2016 Bariatric Surgery Volume (estimated)
VA Boston Healthcare System	1	25	25
VA Ann Arbor Healthcare System	11	55	100
VA Palo Alto Healthcare System	21	30	40
VA Long Beach Healthcare System	22	10	20

Patient eligibility criteria will be determined by electronic data abstraction using CDW:

- Bariatric surgery at one of the 4 VA sites
- Laparoscopic Roux-en-Y gastric bypass (RYGB) or laparoscopic vertical sleeve gastrectomy (SG) six to 18 months prior to the time of data pull
- No procedures to prevent gastric cancer
- No revisional bariatric surgery

The list of patients meeting those criteria will also include full name, social security number, address, phone number, surgery type, and surgery date. Eligible patients will receive a recruitment letter from study staff at the Madison VAMC. Two weeks after recruitment letters are mailed, the project coordinator (PC) will call patients to confirm eligibility, describe the study and obtain telephone consent. If a patient consents to be in the study, a consent form will be sent to their address to review. Once patients have provided consent, the PC will administer several baseline measures orally and schedule patients for their first intervention call. This first screening, consent, and baseline measures call will not be audio-recorded. Responses will be recorded in RedCap. All subsequent intervention calls and participant interviews will be recorded but not transcribed. Instead, relevant notes from the intervention calls and the

Development of a weight maintenance intervention for bariatric surgery patients

participant interviews will be recorded in RedCap. We will remind each participant that they are being recorded on each call, and obtain their verbal consent for recording. Patients may opt out of the study at any time, as indicated in our telephone scripts.

Additional patient eligibility criteria will be determined by telephone screening:

- English as preferred language
- Regular access to a telephone
- No hearing impairment
- No cancer not in remission

Maintenance intervention.

The first intervention telephone call will occur one week following the baseline assessment. Calls will be made weekly in the first month (weeks 1, 2, 3, 4) and biweekly calls during months 2-4 (weeks 6, 8, 10, 12, 14). The intervention will be scripted to ensure reproducibility and to facilitate dissemination and implementation.

Intervention content. The goal of this intervention is to increase adherence to recommendations that patients are already receiving from their bariatric team as part of standard of care. The first 4 calls of the intervention will review key concepts typically taught to patients in a bariatric surgery program, including specific recommendations for diet, physical activity, and vitamin/mineral supplementation. Subsequent calls will address maintenance skill building and anticipatory problem solving based on the processes outlined in our conceptual model and operationalized in our MAINTAIN protocol. Relapse prevention planning will help patients identify situations in which overeating is common in the bariatric population (e.g., loss of control eating related to emotions, disinhibition). These four areas and their intervention implications are provided in Table 3.

Table 3. Incorporating Behavior Maintenance Strategies into the Weight Maintenance Intervention

Strategy	Intervention Implication
Satisfaction with outcomes of behavior change	✓ Patients list the perceived benefits and cost of having changed their behavior ✓ Patients reflect on satisfaction with past outcomes
Self-monitoring	✓ Patients identify frequency of weighing ✓ Patients identify method for logging weight ✓ Patients develop threshold for determining when a lapse occurs and return to dietary self-monitoring if this threshold is exceeded
Recovery self-efficacy/relapse planning	✓ Patients prepare contingency plans for high-risk situations ✓ Patients imagine and role-play responses for hypothetical situations
Primary source of support is social network	✓ Patients identify supportive members of their social networks. ✓ Patients share goals with spouses, friends, coworkers ✓ Patients suggest specific supportive behaviors (e.g., check-in calls, exercise dates)

Measures. Our tracking database will capture the number of recruitment letters mailed, number of recruitment calls attempted and completed, number of patients consented, number of intervention calls delivered, and number of outcome assessment calls completed. As each

Development of a weight maintenance intervention for bariatric surgery patients

intervention call will be recorded, we will also have data on the duration of each call. The RD will record the amount of time spent preparing for the call and conducting any follow-up activities. The following measures will be administered by telephone at weeks 0 and 16. Each patient will receive \$25 for each assessment.

Recovery self-efficacy refers to confidence to get back on track once relapse has occurred. We will measure recovery self-efficacy for dietary behavior and physical activity separately using 3-item measures developed by Schwarzer.¹ Response scales range from 1 (*not at all true*) to 4 (*very true*). Internal consistency for the diet measure of 0.93 has been reported, and 0.71 for the exercise measure.

Satisfaction with outcomes of weight loss. Five items will assess satisfaction with outcomes of changes in the domains of enjoyment of food, health, physical attractiveness, fit of clothes, physical fitness, ability to complete tasks requiring physical exertion, social life, and positive feedback about weight loss.² Response scales range from -4 (I am extremely unhappy about this change) to +4 (I am extremely happy about this change). We obtained internal consistency of 0.86 in our MAINTAIN trial.³

Self-monitoring of weight. A single item will assess frequency of self-weighing during the intervention (During the last four months, how often did you weigh yourself? *Daily, nearly every day, 3 or 4 times a week, once or twice a week, 2 or 3 times a month, once a month, less than once a month, never*)

Weight from EMR. We will calculate and report % weight loss and % excess weight loss, both from start of the intervention and prior to surgery, as these outcomes are important to bariatric surgeons.

Dietary intake will be assessed with 24-hour recalls conducted by the intervention registered dietitian. We will use the VA-approved Food Processor Software on (staff name) located in (location).

Daily physical activity will be assessed by the short version of the International Physical Activity Questionnaire (IPAQ).⁴ Analyses will focus on total physical activity as well as walking given that moderate or vigorous physical activity may not be feasible for this population.

Qualitative interviews to assess experience with the intervention. Semi-structured qualitative interviews will be conducted within two weeks of the final outcome assessment by [name] or [name] or the PC. A semi-structured interview guide will be created, organized around the theoretical constructs indicated in our model. We will conduct interviews with approximately 20 patients. Participants will receive \$25 for completing the qualitative interview.

Analyses.

Aim 1: Refine telephone intervention scripts to address dietary, mobility, and behavioral issues specific to bariatric surgery patients.

During study start-up, the team will have weekly calls in which intervention content is discussed and modified (e.g., a threshold for indicating relapse will be identified). The RD will conduct self-study and receive training from [name] in dietary issues specific to bariatric surgery patients. All intervention calls will be recorded. Each week, Drs. [name] and [name] and the RD will meet to review calls. [name] will listen to a portion of the calls as well. All calls for

the first 5 patients enrolled will be reviewed so that changes to the script can be made if necessary. The script will be revised iteratively until the team feels that patients understand and can engage with the content. Changes may be made to enhance comprehension of intervention material, ability to engage in the recommended behavioral skills, or to address any clinical issues that are identified. The final product from this aim will be a standardized intervention script that will be used in a future IIR to evaluate the efficacy of the intervention.

Aim 2: Evaluate feasibility of conducting a multi-site trial, as indicated by recruitment and outcome assessment rates.

As stated previously, we will use an electronic data pull to identify patients who have had surgery as well as their surgery date. We will create a custom tracking database that will import data from the data pull and create a flag that alerts study staff when patients are due for each intervention call. We will examine the dates of surgery to determine how frequently cases are performed.

From our tracking database, we will calculate the recruitment rate as [# of participants who consent to the study/# of patients to whom letters were mailed]. We will further identify the rate of drop-out following consent to inform allocation of effort to recruitment in the future IIR. The outcome assessment retention rate will be calculated as [#of participants who complete the 16-week outcome assessment call /number who were eligible upon completion of the baseline assessment].

Aim 3: Evaluate intervention acceptability, as indicated by intervention adherence rates, pre-post changes in weight and process measures, and feedback from post-intervention qualitative interviews.

Intervention adherence. For intervention adherence, we will calculate for each participant the mean (and standard deviation) number of intervention calls that were completed. Given our previous experience with telephone-based interventions, we expect high rates of intervention adherence. In [name] COUPLES trial, which involved 10 monthly telephone calls, the mean number of completed patient calls was 7.9 out of 9. In MAINTAIN, the mean number of completed calls was 6.95 (SD=1.75) out of 8.

Pre-post changes in quantitative measures. Weight measurements will be pulled from the VA CDW files. For each patient, baseline weight will be defined as the closest weight prior to the baseline survey assessment. We will assess the feasibility of this definition. Because of the shortened follow-up for this pilot, we anticipate patients will only have on average 1-3 follow-up weights. We will examine descriptively change in weights as well as each survey construct that is measured during telephone-based assessments. For the psychosocial measures, we will calculate total scores according to author instructions. For all measures, we will calculate descriptive statistics and plot the baseline and follow-up weights/scores, which will provide descriptive information on whether and to what extent patients experienced change. From the descriptive data, we will determine how each construct is operationalized in this patient population (e.g., floor/ceiling effects, skewed or highly variable distributions, etc.). For each variable, we will calculate the standardized difference between means, which will enable us to compare magnitude of changes across different measures. Although we will not be powered to detect statistically significant differences, the confidence intervals will provide information on the potential range of effect sizes, which will inform the power analysis for the future IIR.

Post-intervention qualitative interviews. We will use a directed form of qualitative content analysis to code the interview transcripts,⁵ which will include *a priori* codes (based on theoretical constructs discussed in the interview guide) and emergent codes (anything not covered by the initial codes). Participant reactions to the intervention will be organized for analysis by key

Development of a weight maintenance intervention for bariatric surgery patients

maintenance constructs (i.e., satisfaction with outcomes of behavior change, relapse prevention, self-monitoring, and social support) as well as suggested changes to the intervention. [name] and the PC will use consensus to develop the coding framework.⁶ They will first code transcripts independently and meet to resolve discrepancies through discussion until they agree on definitions and rules for applying the codes (*a priori* and emergent). They will use this process with half of the transcripts and review the findings with the rest of the research team. The PC will then code the remainder of the transcripts and revisit the prior transcripts to make sure that the codes were consistently applied. ATLAS.ti (v. 6.1) will be used to manage coding of transcripts.⁷

Sample size considerations. A power calculation will not be performed given that we are not evaluating statistical significance of the intervention in this pilot; rather, we are seeking an indication of feasibility and acceptability. We will enroll 30 patients, which will be adequate to evaluate the feasibility and acceptability of the intervention.

Safety Monitoring Plan. Study staff will report any adverse event or unanticipated problem to the PI immediately. Study staff will review all such events and determine the likelihood they were due to the study. The PI will report any serious, unexpected, and study-related adverse event or unanticipated problem to the local IRB according to the institution's requirements. The IRB will review all adverse events during continuing review, which will occur at least annually. If a Veteran reports that they are suicidal during a phone call, we will use a standard script given to us by the Madison VA Research Office.

References

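### The interview window is tied to the week-16 assessment and gives no route for patients who withdraw or miss it, so followed literally the interview part of Aim 3 can consist entirely of week-16 completers

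*Combined protocol and SAP*

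**What the plan says.** **Timing and number.** Under Measures, the paragraph on qualitative interviews states that "Semi-structured qualitative interviews will be conducted within two weeks of the final outcome assessment" and that "We will conduct interviews with approximately 20 patients". The Design section states that "Patient outcomes will be assessed at baseline and 16 weeks", so the final assessment is the one at week 16. Elsewhere the interviews are described only as following the intervention, which adds no second window.

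**Loss is foreseen.** The recruitment and consent text under Design says "Patients may opt out of the study at any time, as indicated in our telephone scripts". Analyses, Aim 2, plans a drop-out rate after consent, and a retention rate whose numerator is the number of "participants who complete the 16-week outcome assessment call". The drop-out rate is there to plan recruitment effort for the later trial.

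**Use of the interviews.** Aim 3 names "feedback from post-intervention qualitative interviews" as an indicator of acceptability, alongside call adherence and pre-post changes. The qualitative analysis organises patients' reactions by the maintenance constructs "as well as suggested changes to the intervention".

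**Not stated.** The visible text gives no exit interview, no other interview window, no invitation route for patients who stop or miss week 16, and no rule for choosing the 20. It does not say whether 20 is a chosen subset or the expected uptake.

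**The concern.** Acceptability is easily distorted by selection on retention, because patients who leave or stop answering are plausibly those who found the intervention least acceptable. If staff schedule interviews from completed week-16 assessments, those patients are never approached.

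The omission would also be hard to notice. The interview target could be met in full with nobody heard from the group whose views matter most for revising the intervention. The report could then present interview findings as evidence about the enrolled patients when they describe only those who stayed.

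**Working it through.** The plan derives no figure on this point, so there is nothing to reproduce. Its numbers are 30 enrolled (Sample size considerations) and about 20 interviews (Measures). It gives no expected week-16 retention and no expected interview uptake.

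**Step 1: when completers alone suffice (documents' figures only).** Let m be the number of the 30 who miss week 16. Completers number 30 − m, and they can fill 20 interviews while 30 − m ≥ 20, that is m ≤ 10. The threshold is 10/30 = 33.3%. With m = 12, at most 18 completers could be interviewed. Below the threshold, reaching 20 interviews says nothing about whether any non-completer was included. Under the literal rule the number included is 0 by construction.

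**Step 2: what other invitation rules would yield (assumed inputs).** Assume that m is 3 or 8, that each non-completer agrees independently with probability p between 0.3 and 1.0, and that all completers agree. Let W ~ Binomial(m, p) be the number of willing non-completers.

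- Random 20 from all willing patients: P(at least one) = 1 − Σ_w Binom(w; m, p) × C(30−m, 20)/C(30−m+w, 20).
- All non-completers invited within the same 20: P(at least one) = 1 − (1−p)^m, with expected number mp.

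Worked case, m = 3 and p = 1: 1 − C(27,20)/C(30,20) = 1 − 888030/30045015 = 1 − 0.0296 = 0.970.

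Worked case, m = 3 and p = 0.5: the ratios for w = 0, 1, 2, 3 are 1, 0.2857, 0.0887 and 0.0296, with weights 0.125, 0.375, 0.375 and 0.125. The sum is 0.269, so P = 0.731. Inviting all gives 1 − 0.5³ = 0.875.

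| m | p | Random 20: P(≥1), expected | All invited: P(≥1), expected |
|---|---|---|---|
| 3 | 0.3 | 0.513, 0.63 | 0.657, 0.9 |
| 3 | 0.5 | 0.731, 1.04 | 0.875, 1.5 |
| 3 | 1.0 | 0.970, 2.00 | 1, 3 |
| 8 | 0.3 | 0.909, 1.92 | 0.942, 2.4 |
| 8 | 1.0 | >0.999, 5.33 | 1, 8 |

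**Step 3: smaller losses.** With p = 0.3 and everyone invited, m = 1 gives 0.30 (expected 0.3) and m = 2 gives 1 − 0.7² = 0.51 (expected 0.6). When few are lost and few agree, the yield may well be nobody.

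**Step 4: what does not depend on the week-16 call.** Call adherence is calculated for each participant. Weights come from VA electronic records. Notes from intervention calls are entered in RedCap, and calls are reviewed weekly. A patient who took few calls but completed week 16 can still be interviewed. The gap is therefore confined to patients who withdraw or miss week 16, and to the interview evidence.

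**The case against.** The strongest objection is that the sentence sets a time, not an eligibility condition. A reader might infer that the plan excludes drop-outs from interview, but no text says so. If the final outcome assessment means its scheduled date, someone who missed the call could still be interviewed. The opt-out sentence also points to telephone scripts that are not in the file, and the consent pages were removed. Either might contain an invitation for patients who stop. This stands: the finding is about a rule followed literally and a route absent from the visible text, not a proven exclusion.

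A reader might also infer that Aim 3 as a whole is biased. That is not supported, because the other indicators survive as set out above, and call notes and weekly review give some view of dissatisfaction. They capture only what patients say while they still take calls, however, so they do not replace an interview with someone who has left.

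The probabilities rest on assumed loss and uptake. The nearest evidence, in the Aim 3 text, is mean call completion in two previous trials: 7.9 of 9 (88%) and 6.95 of 8 (87%). That is adherence rather than retention, but it gives no support for a loss as high as 8 of 30 (27%). Low losses would make the yield small.

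Finally, inviting non-completers within a fixed 20 displaces completers, up to 8 of 20 in the upper case with full uptake. Those patients have had less exposure to the maintenance content around which the analysis is organised. This is a real cost. For a small descriptive pilot, interviewing people after the intervention is a defensible choice, and nothing here is contradictory or miscalculated.

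**Conclusion.** The concern holds in a limited form. The stated window supplies no route for patients who withdraw or miss week 16. Applied literally, it allows every interview to come from week-16 completers unless more than 10 of 30 are lost. That threshold uses only the plan's own figures. In that case the interview-based acceptability conclusion covers completers only, and the plan does not say so.

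How much would be gained by changing the rule is uncertain. Over the main assumed range (3 to 8 lost, uptake 0.3 to 1.0), inviting all non-completers gives a chance of at least 0.66 of hearing one or more. With only one patient lost and uptake 0.3, the chance falls to 0.30. These are illustrations, not forecasts.

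This is a worthwhile, inexpensive improvement to the design, not an error in it. Confidence is medium, because the scripts and consent form cannot be seen.

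**What to change.** - Set the interview window from the scheduled week-16 date, whether or not the assessment is completed. For patients who stop earlier and agree to be contacted, set it from the point of stopping.
- State who is invited, and invite every contactable non-completer within the same 20 or so interviews.
- Report how many interviewees were non-completers. If none were interviewed, limit the interview-based acceptability conclusion to week-16 completers.
- If the telephone scripts or consent form already provide such a route, state it in the protocol.

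The number of interviews, the staff and the $25 payment stay the same. The costs are a few more contact attempts, some refusals, possibly a small change to script or consent wording, and the loss of some completer interviews to patients who saw less of the maintenance content. The yield may be one person or none.

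### The confidence interval of an uncontrolled pre-post change is offered as the effect-size range for powering the future IIR, but it does not estimate a between-arm effect

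*Combined protocol and SAP*

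**What the plan says.** The Design section states: "This pilot study will be a within-person, pre-post design". Outcomes are taken at baseline and 16 weeks while usual follow-up care goes on. Sample size considerations gives the size, "We will enroll 30 patients", reports no power calculation, and limits the purpose: "we are seeking an indication of feasibility and acceptability".

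Under Aim 3, pre-post changes in quantitative measures, the effect measure is defined: "For each variable, we will calculate the standardized difference between means, which will enable us to compare magnitude of changes across different measures". After noting that the pilot is not powered for significance, the paragraph ends by giving the intervals a further use: "the confidence intervals will provide information on the potential range of effect sizes, which will inform the power analysis for the future IIR".

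The future IIR is described only under Aim 1, where the product of the pilot is "a standardized intervention script that will be used in a future IIR to evaluate the efficacy of the intervention". Its comparator and allocation are not stated. The predecessor trial, MAINTAIN, is described in Background and Significance as involving "randomization to maintenance intervention or usual care among patients losing at least 4 kg in the initiation phase".

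No section provides a concurrent or historical control, an estimate of change under usual care, or a conversion from pre-post change to a between-arm effect.

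**The concern.** A controlled trial is powered on a difference between arms. A one-group change mixes the intervention's effect with whatever would have happened anyway under usual care. The interval around it carries the sampling error of that mixture and makes no allowance for background change. The caveat about power concerns precision and does not touch this.

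The protocol itself expects background change in weight. The Purpose section says regain after surgery is common, and Background and Significance describes the benefit as less regain. A successful maintenance intervention could therefore show no pre-post change at all, and the planned interval would then present a range of effects centred on zero. Eligibility at 6 to 18 months after surgery could also leave room for continued loss under usual care, in which case the pre-post change would overstate the benefit. The sign of the error cannot be settled from the documents.

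What is at stake is one stated input to the next trial's sample size. The pilot's feasibility and acceptability results, its conduct and its participants are not affected.

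**Working it through.** **The plan's own figure.** There is nothing to reproduce. The 30 patients are stated without alpha, power, effect size or SD. What follows is illustration on assumed values.

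**Inputs.**
- From the documents: one group, two time points, 30 enrolled. Complete pairs may be fewer, since the plan will "identify the rate of drop-out following consent", so 24 is also shown (assumed).
- Assumed: the IIR is controlled; data are normal; pre and post SDs are equal; pre-post correlation r is 0.5 or 0.9; background change b is 0.1, 0.2 or 0.3. Effects are in score-SD units with benefit positive, so the SD of change is √(2(1−r)): 1.000 at r = 0.5 and 0.447 at r = 0.9.

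**Step 1. What each study estimates.** The pilot estimates the intervention-arm change. The IIR effect is that change minus the control-arm change. The two differ by b, whatever the sample size.

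**Step 2. The intervals the pilot would give.** Noncentral-t 95% interval for change divided by SD of change, multiplied by √(2(1−r)), 30 pairs:

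| Pilot change | r = 0.5 | r = 0.9 |
|---|---|---|
| 0.5 | 0.12 to 0.88 | 0.29 to 0.70 |
| 0 | −0.36 to 0.36 | −0.16 to 0.16 |

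Suppose 0.3 of the 0.5 is background; the true effect is 0.5 − 0.3 = 0.2. Suppose instead that the pilot shows 0 and controls worsen by 0.3; the true effect is 0 − (−0.3) = 0.3. At r = 0.5 the intervals include both effects, and at r = 0.9 they exclude both. The switch comes at r of about 0.72 in the first case and 0.65 in the second (0.79 and 0.72 with 24 pairs).

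**Step 3. How often the interval contains the between-arm effect.** For the ordinary paired 95% interval, coverage is P(|T| ≤ t₀.₉₇₅,ₙ₋₁), where T is noncentral t on n−1 degrees of freedom with noncentrality b√n / √(2(1−r)). Example: n = 30, r = 0.5, b = 0.2 gives 0.2 × 5.477 / 1.000 = 1.095; the critical value is 2.045 and coverage is 0.815. The sign of b does not matter.

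| Pairs | r | b = 0.1 | b = 0.2 | b = 0.3 |
|---|---|---|---|---|
| 24 | 0.5 | 0.924 | 0.844 | 0.709 |
| 24 | 0.9 | 0.817 | 0.445 | 0.118 |
| 30 | 0.5 | 0.917 | 0.815 | 0.645 |
| 30 | 0.9 | 0.780 | 0.342 | 0.056 |
| 60 | 0.5 | 0.881 | 0.668 | 0.372 |

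At b = 0, coverage is 0.950. The 60-pair row is not a sample this pilot will have. It shows that more data lowers coverage, as happens when an interval targets a different quantity. A simulation of 100,000 runs at n = 30 gave 0.813 and 0.643 (r = 0.5) and 0.340 and 0.055 (r = 0.9) for b = 0.2 and 0.3.

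**Step 4. Consequence for the IIR's size.** With SD of change 1, two-sided alpha 0.05, power 0.80 and equal arms, n per arm = 2 × ((1.960 + 0.842)/d)².
- A pilot change of 0.5 taken as d: 62.8, so 63 per arm.
- Controls also improve by 0.2, so d = 0.3: 174.4, so 175 per arm. Power at 63 per arm is 39%.
- Controls worsen by 0.2, so d = 0.7: 32.04, so 33 per arm. Power at 63 per arm is 98%.

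**The case against.** The strongest reply is that the plan claims little. It says the intervals will inform the power analysis, not fix its target difference or serve as its only input, and it limits the pilot to feasibility and acceptability. This stands, and it confines the point to one clause. It does not rescue the clause, because a range that omits the control-arm change should not be presented as the range of effects for a controlled trial.

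Second, the IIR's design is not in the documents. That also stands: a controlled IIR is an inference from its efficacy purpose and from the randomized predecessor.

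Third, the two quantities coincide if background change is zero, and the documents speak of background change only for weight, without a rate. For self-efficacy, satisfaction, diet and activity they give no expectation either way. That is fair, but agreement would then rest on an unexamined assumption.

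Fourth, the illustrations use assumed inputs, and the lowest coverage needs both a high correlation and a large shift. At r = 0.5 and b = 0.1, coverage is 0.917, close to nominal. This stands too, and is why a range is shown. Finally, the pilot's follow-up is short, so its SDs and correlation may themselves need care before being carried into a longer trial.

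**Conclusion.** The concern holds. In a one-group design the stated interval estimates the intervention group's own change, and nothing in the plan connects that to the effect a controlled IIR would test. The conclusion rests on one assumption about the future trial, that it will have a control arm. The size of the error is not determined by the documents: in the cases shown for 30 pairs, coverage of the between-arm effect ranges from near nominal (0.917) to almost none (0.056), and the required IIR size can move either way. The change should be made, but it concerns a stated use of the results. The 30-patient target and the feasibility aims stand.

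A lesser point needs clarifying: the SD used to standardize changes is not named. With equal SDs and r = 0.9, dividing by the SD of change gives a value 1/√(2 × 0.1) = 2.24 times that from the score SD, so comparisons across measures with different correlations depend on the choice.

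**What to change.** Keep the caveat about power and replace the rest of the closing sentence of the Aim 3 paragraph on pre-post changes with text such as:

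> For each measure we will report the number of complete pairs, the raw mean change with a paired 95% confidence interval, the SD of scores and of change, and the pre-post correlation. The SDs and correlation, together with retention and the availability of weights, will inform the IIR power analysis. The IIR target difference will be a minimally important between-arm difference or will come from external controlled data, and not from the change seen in this pilot.

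As a secondary clarification, state that changes are standardized by the baseline SD when magnitudes are compared across measures. Other denominators are defensible; what matters is that one is named.

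The cost is one revised sentence and a few summary statistics from data already planned, with no new data collection. The pilot claims slightly less, and the IIR team must justify its target difference from another source, which the present documents do not identify.
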